8.4 VISIT 3 AND ONWARDS (INFUSION 3 OF EMAPALUMAB AND ONWARDS)

The following assessments are to be performed pre-infusion at all visits from Visit 3 onwards, unless specified differently:

Clinical Assessment:

- Vital signs, including body temperature, heart rate, blood pressure, and oxygen saturation
- Physical examination, including as a minimum, weight, spleen and liver size (by abdominal palpation), and neurological examination
- Assessment of clinical response every 2 weeks

Search for infections:

- TB by PCR (every 4 weeks)
- Infection search & monitoring in case of suspicion of infection or if there is an active infection at screening/baseline to monitor evolution of viral load and positivity for an identified pathogen
- Atypical mycobacteria, Histoplasma capsulatum, Shigella, Salmonella, Campylobacter, Leishmania - if an infection is suspected

Laboratory:

- CBC with differential count (including large unstained cells count, whenever performed as routine)
- Coagulation tests: activated partial thromboplastin time and/or ratio, prothrombin time and/or INR, D-dimers and fibrinogen
- Biochemistry: glucose, ferritin, CRP, liver function (AST, ALT, γGT, LDH, ALP, bilirubin), renal function (albumin, creatinine and urea) and triglycerides (fasting whenever possible)

Imaging:

- Abdominal ultrasound with spleen longitudinal measure (every 2 weeks during emapalumab treatment)
- Chest X-ray in case of clinical suspicion of pulmonary infection or to monitor existing abnormalities

Safety:

Recording of any AEs occurred since last visit

PK:

 Emapalumab serum concentration (every other infusion starting from Visit 3)

PD:

 CXCL9, CXCL10, sCD25, total IFNγ (every other infusion starting from Visit 3)

Immunogenicity:

ADAs (only at Week 4, together with a PK sample)

IMP Handling:

Preparation, dispensing, and accountability

The infusion will be administered over a period of 1 to 2 hours twice a week (not more than 4 days apart). Monitoring of heart rate and oxygen saturation will be performed, with recording of values at 30 minutes after the beginning of the infusion. If this is the first infusion at an increased dose of emapalumab, and/or

Study NI-0501-09 NI-0501 in Primary HLH Page 53 of 92

patient has experienced an infusion-related reaction, blood pressure, heart rate and oxygen saturation are to be collected every 15 minutes during and until the end of the infusion.

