The following assessments are to be performed post-infusion at Visit 3 and onwards:

Vital sign assessment:

 Heart rate, oxygen saturation, blood pressure and temperature at the end of the infusion, 1 hour and 2 hours after completion of emapalumab infusion

PK:

 Emapalumab serum concentration (every other infusion starting from Visit 3)

Clinical Assessment:

 QOL questionnaire - PedsQL[™], Pediatric Quality of Life Inventory[™] (at Visit 3 only)

During treatment, emapalumab and biomarker concentrations may be measured in other matrices, such as CSF or BAL, if samples obtained in procedures which are performed for diagnostic/therapeutic purposes can also be available for these exploratory investigations, and if clinically indicated.

8.5 WEEK 8 ASSESSMENT VISIT (3 DAYS AFTER WEEK 8 INFUSION) AND END OF TREATMENT VISIT (3 DAYS AFTER LAST EMAPALUMAB INFUSION)

These visits will include a full patient's assessment.

The Week 8 Assessment Visit will be performed 3 (± 1) days after the last Week 8 emapalumab infusion. If treatment with emapalumab is completed before Week 8, only an EOT visit will be performed 3 (± 1) days after the last infusion.

For patients continuing treatment beyond Week 8, an EOT visit will be conducted 3 (± 1) days after the last emapalumab infusion.

The following assessments are to be performed at the Week 8 Assessment Visit and at the EOT Visit:

Clinical Assessment:

- Vital signs, including body temperature, heart rate, blood pressure, and oxygen saturation
- Physical examination, including as a minimum, weight, spleen and liver size (by abdominal palpation), and neurological examination
- Assessment of clinical response
- QOL questionnaires PedsQL[™], Pediatric Quality of Life Inventory[™],
 BASES (BASES only at EoT and if HSCT is planned)

Procedure:

ECG (only at EOT)

Search for infections:

- TB by PCR (if not performed within the last 4 weeks)
- Infection search & monitoring in case of suspicion of infection or if there is an active infection at screening/baseline to monitor evolution of viral load and positivity for an identified pathogenAtypical mycobacteria, Histoplasma Capsulatum, Shigella, Salmonella, Campylobacter, Leishmania – only if an infection is suspected

Study NI-0501-09 NI-0501 in Primary HLH Page 54 of 92

Laboratory:

 CBC with differential count (including large unstained cells count, whenever performed as routine)

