6.1.4. Handling of Dropouts or Missing Data

[figure not shown]
While all possible efforts will be made to ensure that patients stay in the study and all data is collected as scheduled, the occurrence of missing data cannot be completely eliminated.

Rules for handling missing or partial AEs or birth dates are described in Section 6.1.10

For defining the primary efficacy endpoint (Overall Response, see Section 6.1.9.4 for definition), values of some parameters may be missing, thus impacting the response assessment. Imputation rules for assessing disease response at EOT or Week 8 (whichever occurs earlier) and throughout the study have been pre-defined as follows. Note: Imputed values will be flagged in the listings for all endpoints where applicable.

Response at EOT or Week 8 (whichever occurs earlier):

- Missing data at EOT/Week 8 for the parameters relevant to assessment of Overall Response will be imputed by the closest available value from the EOT/Week 8 target day (as per Table 1 and Table 2) up to 8 days, provided upper window limit is before start of conditioning. For body temperature, in the event of repeated measures recorded on the same study day, the highest value will be selected.
- No imputation will be applied if no value is available within the time of the EOT/Week 8 target day up to 8 days. That parameter will be viewed as missing and complete response will not be assigned, even if all other parameters are normal.
- Values recorded at both scheduled and unscheduled visits will be considered.

• If all parameters are unable to be imputed then the overall response assessment will be recorded as missing.

Response throughout the study:

- For secondary time to event analyses (e.g., duration of response, time to response), both scheduled and unscheduled visits will be used for assessment of response.
- If a numerical parameter (i.e. Body Temperature, D-Dimer, Fibrinogen, Ferritin, Platelets, Neutrophils) needed for the response assessment is missing, the midpoint approach will be used to estimate the missing value i.e., the last observed value before the missing period will be averaged with the first value available after the missing period. This rule will be applied to parameter values missing for a period of up to a maximum of 7 consecutive days.

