6.1.5. Analysis Visit Windows

Statistical analyses will be based on the windowing displayed in Table 1 (patients with a

treatment duration less than 8 weeks, i.e. < 56 days) and Table 2 (patients with a treatment duration of 8 weeks or more, i.e. >= 56 days).

However, imputation of missing data will be applied as described in Section 6.1.4.

Visit Name		Tougot dou	Analysis visit window			
		Target day	From SD	To SD		
Baseline				ded prior to the first dose apalumab		
Study Day 0 (free mapal		1	1	1		
Study	Day 3	4	2	5		
Study Day x		Study Day x + 1 day	Target day – 1 day	Target day + 1 day		
	Study Day n-1	Study Day x +1 day	Target day – 1 day	Day of last infusion of emapalumab		
a) EOT visit available	EOT / Week 8	EOT visit	Day of last infusion of emapalumab +1	EOT visit		
	EOT	EOT visit	EOT visit	EOT visit		
	Study Day n-1	Study Day x +1 day	Target day – 1 day	Day of last infusion of emapalumab – 1 day		
b) no EOT visit available	EOT / Week 8	Start day of last infusion *	Start day of last infusion *	End day of last infusion *		
	EOT	Start day of last infusion *	Start day of last infusion *	End day of last infusion *		

[figure not shown]
* Start and End date of infusion are in most of the cases the same date.

- a) If an EOT visit was performed and treatment duration was < 8 weeks (i.e. < 56 days), the day of EOT visit will be assigned as EOT/Week 8 analysis visit and as EOT visit prior to start of conditioning.
- b) If no EOT visit was performed and treatment duration was < 8 weeks (i.e. < 56 days), the day of last infusion will be assigned as EOT/Week 8 analysis visit and as EOT visit prior to start of conditioning.

		-	Analysis visit window			
Visit Name		Target day				
			From SD	To SD		
Baseli	ne		Last observation recorded prior to the first dose of emapalumab			
Study Day 0 (firs	t infusion of	1	1	1		
emapalur		1	1	1		
Study D	ć	4	2	5		
Study D	•	7	6	8		
Study D	•	10	9	11		
Study Da	2	13	12	14		
Study Da	2	16	15	17		
Study Da		19	18	20		
Study Da	•	22	21	23		
Study Da		25	24	26		
Study Da		28	27	29		
Study Da		31	30	32		
Study Da		34	33	35		
Study Da	•	37	36	38		
Study Da	2	40	39	41		
Study Day 37 Study Day 42		43	42	44		
Study Da	•	46	45	47		
Study Day 49 Study Day 48		49	48	50		
Week 8 is the last week prio			_	20		
	Study Day 51	52	51	Day of last infusion of emapalumab		
a) EOT visit available	EOT / Week 8	EOT visit	Day of last infusion of emapalumab + 1 day	EOT visit		
	EOT	EOT visit	EOT visit	EOT visit		

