	Study Day 51	52	51	Day of last infusion of emapalumab - 1 day		
b) no EOT visit available	EOT / Week 8	57	Day of last infusion of emapalumab	Day of last infusion of emapalumab + 6 days		
	ЕОТ	Start day of last infusion *	Start day of last infusion *	End day of last infusion *		

Table 2: Treatment Visit Windows, treatment duration >= 8 weeks

Visit Name		Torget day	Analysis visit window				
		Target day	From SD	To SD			
Week 8 is not th	Week 8 is not the last week prior to EOT visit or last infusion (subsequent weeks (x to n))						
	Week x	Week (x*7) +1	Target day – 3 days	EOT visit – 1 day			
a) EOT visit available	EOT / Week 8	57	54	60			
EOT		EOT visit	EOT visit	EOT visit			
	Week x	Week (x*7) +1	Target day – 3 days	Day of last infusion of emapalumab – 1 day			
b) no EOT visit available	EOT / Week 8	57	54	60			
ЕОТ		Start day of last infusion *	Start day of last infusion *	End day of last infusion *			

* Start and End date of infusion are in most of the cases the same date.

If treatment duration was ≥ 8 weeks (i.e. ≥ 56 days) the visit within the analysis visit window of 54 and 60 days and closest to the target day will be assigned as EOT/Week 8 analysis visit.

- a) If an EOT visit was performed the day of EOT visit will be assigned as EOT visit prior to start of conditioning.
- b) If no EOT visit was performed the day of last infusion will be assigned as EOT visit prior to start of conditioning.

[figure not shown]

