Partial Response	 Partial Response is adjudicated if: At least 3 of the HLH clinical and laboratory abnormalities (including CNS abnormalities) meet the above mentioned criteria for "Complete Response" In the case of "reactivated patients" who enter the study with 3 abnormal HLH features, Partial Response is adjudicated if at least 2 parameters normalize 	If a patient is not considered as "reactivated" or a patient is considered "reactivated" with 4 or more abnormal HLH features upon entry to the study and at least 3 of the HLH clinical and laboratory abnormalities (including CNS abnormalities) meet the above-mentioned criteria for "Complete Response" Partial Response is adjudicated.
	 In case of reactivated patients who enter the study with 2 abnormal HLH clinical and laboratory parameters only, Partial Response is adjudicated if one of the 2 parameters normalizes There is no progression of other aspects of HLH disease pathology 	For all patients: no progression of other aspects of HLH disease pathology is assessed by absence of AEs indicating organ failure including no worsening of sCD25 levels.

Response for Primary Endpoint	Definition	Additional Clarifications
HLH Improvement	 HLH Improvement is adjudicated if: Improvement (>50% change from baseline or normalization) of at least 3 HLH clinical and laboratory abnormalities (including CNS abnormalities). In the case of "reactivated patients" who enter the study with only 2 abnormal HLH features, a change from baseline greater than 50% for both will define HLH as improved. 	 Definition of 50% improvement from baseline: Spleen size decreased by 50%, as recorded in cm from costal margin at physical examination. Absolute Neutrophil Count increased by 50%, if G-CSF has not been administered in the previous 4 days and Platelet count increased by 50%, if no platelet transfusion has been administered in the previous 4 days Ferritin decreased by 50% Fibrinogen increased by 50% or D-Dimer decreased by 50% Normalization of CNS abnormalities = normal neurological assessment by investigator without findings in brain imaging (Brain MRI/Brain CT/cranial ultrasound), CSF analysis or AEs indicative of "CNS involvement" or "CSF abnormalities"
No Response	If a subject does not meet the criteria for at least HLH improvement, response is categorized as "No Response"	
Abbreviations: CNS, c lymphohistiocytosis	entral nervous system; CSF, cerebrospinal fluid; G-CSF, gr	anulocyte-colony-stimulating factor; HLH, hemophagocytic

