* end of study, or any time during follow-up period (including withdrawal of consent)				

Table 11: Event-Free Survival

• Duration of Response (i.e. maintenance of response achieved at any time during the study until EOT) is defined as the total elapsed time from achievement of first Overall Response to first loss of response, pending the duration of this response is at least 4 days. If the first observed response does not last for at least 4 days, then the next response period will be considered. Similarly, loss of response should persist for at least 4 days, otherwise the next loss of response period will be considered. Patients who are in response at EOT will be censored at that date. Patients who do not achieve at least HLH improvement once between the date of first dose and EOT will be excluded from the analysis.

The analysis start and end dates and the censoring rules for calculation of duration of response are described in the following scheme:

Situation	Outcome (event or censored)	Analysis start date	Analysis end date
Maintained loss of overall response	Event	Date of first response ²	Date of loss of overall response ²
Death for any cause	Event	Date of first response ²	Date of death
In response at the end of the observation period ¹	Censored	Date of first response ²	Last known response

Table 12: Duration of Response

AD-ST-33.06 Effective date: 12-Nov-2020

¹ end of treatment without conditioning, or start of conditioning for HSCT, or early termination (including withdrawal of consent);

[figure not shown]
² last for at least 4 days

- Cumulative Duration of Response = Total time in response from the first achievement of an Overall Response until HSCT conditioning (or EOT if the patient did not have HSCT performed). Considering patients who achieve a response, lost that response, and then achieve it subsequently, the total time in response will be calculated by adding together these separate periods in response. Patients who do not achieve response at least once between the date of first dose and the time of conditioning start are excluded from the analysis.
- Percent days in response = Cumulative response duration divided by number of days from first infusion until HSCT conditioning (or EOT if the patient did not have HSCT performed).

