16.4. Adverse Events Indicating Organ Failure by MedDRA Preferred Term and Code

Preferred Term Code	Preferred Term
10007554	Cardiac failure
10007556	Cardiac failure acute
10060953	Ventricular failure
10024119	Left ventricular failure
10063081	Acute left ventricular failure
10039163	Right ventricular failure
10063082	Acute right ventricular failure
10051093	Cardiopulmonary failure
10038695	Respiratory failure
10001053	Acute respiratory failure
10019663	Hepatic failure
10000804	Acute hepatic failure
10077305	Acute on chronic liver failure
10019845	Hepatorenal failure
10038435	Renal failure
10077361	Multiple organ dysfunction syndrome
10053159	Organ failure
10010264	Condition aggravated

Table 21: AE Preferred Terms for Organ Failure

Progression of other aspects of HLH disease pathology (i.e. worsening of disease, as assessed by absence of AEs indicating organ failure) is fulfilled during the time period in which any of the above listed AEs is present and partial response cannot be adjudicated even if other criteria were fulfilled.

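### The primary analysis has no rule for death before the EOT visit: a patient with no EOT visit is scored on last-infusion-day values and can count as a responder; sensitivity analysis 2 is also assigned to two different sets

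*SAP*

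**What the plan says.** **Endpoint and test.** SAP 8.1 tests Overall Response at EOT or Week 8, whichever is earlier. The rate is responders divided by all patients in the All Treated set, tested against 40% with an exact binomial test at one-sided 0.025.

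**EOT visit.** Protocol 8.5 places the EOT visit 3 (±1) days after the last infusion: "If treatment with emapalumab is completed before Week 8, only an EOT visit will be performed".

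**No EOT visit.** In SAP 6.1.5, Table 1 (treatment under 56 days), rule (b) states that "the day of last infusion will be assigned as EOT/Week 8 analysis visit and as EOT visit prior to start of conditioning". In Table 2 (56 days or more), the no-EOT row where Week 8 is the last week has target day 57 and a window from the last infusion to "Day of last infusion of emapalumab + 6 days".

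**Missing data.** Under SAP 6.1.4, missing response items "will be imputed by the closest available value from the EOT/Week 8 target day", up to 8 days. Death is not mentioned. If no item can be filled, response is recorded as missing.

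**Adverse-event bar.** SAP Table 6 rules out Complete and Partial Response when an organ-failure event is present. SAP 16.4, whose list includes 'Condition aggravated', says of such periods that "partial response cannot be adjudicated even if other criteria were fulfilled". HLH Improvement in Table 6 requires "Improvement (>50% change from baseline or normalization) of at least 3 HLH clinical and laboratory abnormalities", with no such bar.

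**Deaths and withdrawals.** Deaths are non-responses only in sensitivity analyses 1 and 4 (SAP 8.1), and neither states a period. For sensitivity analysis 2 (early withdrawal as non-response), SAP Table 3 marks only the Evaluable columns, while SAP Table 15 lists All Treated.

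**The concern.** A patient who dies within days of an infusion has no EOT visit, so rule (b) moves the assessment back to a day when the patient was alive. If the values that day meet any response category, the death counts as a success in the primary result. In a single-arm test against a fixed 40%, that can only push the result upward.

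The two sensitivity analyses that count deaths as failures do not carry the primary p-value. They also give no time limit, although follow-up runs to 1 year after HSCT or the last infusion. Read literally, analysis 1 could fail a Week 8 responder who died many months later, so it does not isolate the deaths at issue.

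The mismatch on sensitivity analysis 2 is a separate and smaller matter. The Evaluable set requires at least 3 consecutive infusions (SAP 5). Run as Table 3 has it, the withdrawal check leaves out the earliest withdrawals, which are the ones it most needs.

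**Working it through.** **1. Tracing the route.**
- Treatment under 56 days, death 1 to 4 days after the last infusion (3+1=4), no EOT visit: Table 1 rule (b) scores the last-infusion day.
- Data exist that day. Protocol 8.4 says "The following assessments are to be performed pre-infusion at all visits from Visit 3 onwards, unless specified differently", and the list covers vital signs, spleen palpation, blood count, coagulation and ferritin. Imputation is usually not needed.
- An organ-failure or 'Condition aggravated' event present that day blocks Complete and Partial Response. It does not block HLH Improvement, which is enough for Overall Response. An event starting after the scored day does not count.
- Not affected: patients with an EOT visit (scored there) and patients treated past Week 8 (scored on days 54 to 60). A death with no usable values is recorded as missing. Because the denominator is all treated patients, it would in effect not count as a response, although SAP 8.1 does not say so.

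**2. The Table 2 branch.** SAP Table 4 defines duration as last minus first infusion date, plus 1. A duration of at least 56 days puts the last infusion on analysis day 56 or later. The target is day 57, so last-infusion values precede the target by at most 57−56=1 day. This branch is nearly empty.

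**3. Reproducing a stated figure.** Inputs: null rate 0.40, one-sided alpha 0.025, n=34 minimum and 41 maximum (SAP 3.2 and 8.1). Formula: p = P(X≥r | n, 0.40), X binomial. The protocol's background section reports 64.7% of 34, i.e. 22/34, with p=0.0031 in the earlier study. The formula gives 0.0031, so the test is the same. (At n=34 it has 82.6% power at a 65% rate, against the stated 85%. That is a separate matter and does not affect this point.)

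**4. Cutoffs.**

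| n | Responders | p | Result |
|---|---|---|---|
| 34 | 20 | 0.0205 | significant |
| 34 | 19 | 0.0444 | not significant |
| 41 | 24 | 0.0126 | significant |
| 41 | 23 | 0.0270 | not significant |

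One reclassified patient changes the verdict only if the count is exactly at the cutoff. At the planned 65% rate the probability of that is P(X=20 | 34, 0.65)=10.4%, or P(X=24 | 41, 0.65)=8.7%.

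**5. Conditional effect on the chance of a positive test.** The documents give no number of deaths before EOT/Week 8. The 10 of 34 deaths in the earlier studies cover all follow-up. Assume m=1 or 2 such patients, and a rate of exactly 40% when deaths are failures. The scored rate is then 0.40+m/n.

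| n | m | Scored rate | P(positive) |
|---|---|---|---|
| 34 | 0 | 0.4000 | 2.0% |
| 34 | 1 | 0.4294 | 4.5% |
| 34 | 2 | 0.4588 | 9.0% |
| 41 | 0 | 0.4000 | 1.3% |
| 41 | 1 | 0.4244 | 2.8% |
| 41 | 2 | 0.4488 | 5.5% |

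**6. Sensitivity analysis 2.** Analysis 4, in All Treated, makes failures of withdrawals plus deaths plus patients given other HLH treatment. If analysis 4 is significant, analysis 2 in All Treated must be too. If analysis 4 fails, the part due to withdrawal is not isolated.

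**The case against.** Rule (b) is an explicit, pre-specified scoring rule. Under it the assessment is the last-infusion day, the patient is alive then, and death comes afterwards. The endpoint is response at end of treatment, not survival to a visit three days later. The secondary response endpoint is also taken at the last infusion when there is no HSCT. On that reading nothing is misclassified and the test keeps its size of 2.0% or 1.3%. Sensitivity analyses 1 and 4 already report the alternative with the same test in All Treated, and having no time limit makes them harsher, not softer. On sensitivity analysis 2, SAP 8.1 defers to Table 3, so it could be said that Table 3 governs.

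Most of this stands, and it limits the point. It does not show that the choice was meant to cover death: rule (b) deals with an absent visit for any reason, and the SAP never says that a patient who dies in the EOT window should be scored on earlier values. Deference to Table 3 does not remove the contradiction with Table 15, or the loss of the earliest withdrawals.

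A reader might take Table 12, where "Death for any cause" is an event, as proof that the SAP regards death as failure of response. It is weak support. That table concerns how long an achieved response lasts, and Table 13 (time to response) censors deaths. Table 13 labels even the response row as censored, so it settles little either way.

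**Conclusion.** The point holds in a limited form: the primary analysis has no rule for death before the EOT visit, and Table 1 rule (b) lets such a patient count as a responder. The bias runs upward only. To take this route a patient must be treated for under 8 weeks, have no EOT visit, die soon after an infusion and already meet a response category that day. The number of such patients is unknown, and one of them matters to the verdict only at 20/34 or 24/41.

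Three stronger readings are not supported:
- **That the type I error is inflated to 4.5% or 9.0%.** Those figures need a null redefined with deaths as failures, a true rate of exactly 40%, and an assumed 1 or 2 patients. For the hypothesis the SAP states, size is unchanged.
- **That Table 2 is a second material route.** Its last-infusion values lie within about a day of the target.
- **That the plan ignores deaths.** Sensitivity analyses 1 and 4 count them as failures; what they lack is a time limit.

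The conflict between Tables 3 and 15 is plain on the text and is a reconciliation item. Overall severity: minor to moderate.

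**What to change.** 1. In SAP 6.1.4 and 8.1, state that in the primary analysis a patient with no EOT visit, whose EOT/Week 8 assessment would be scored on last-infusion values, is a non-responder if death occurs within the protocol's EOT visit window (up to 4 days after the last infusion). Use the same limit for Table 1 and Table 2, so that the cutoff does not depend on which table applies.
2. Keep sensitivity analyses 1 and 4, and state the time limit for deaths in each. If analysis 1 is meant as a worst case, say that it counts deaths throughout follow-up; limited to the same 4 days it would largely repeat the new primary.
3. Add last-infusion scoring of these deaths as a further sensitivity analysis, and list the patients concerned. Also list any patient with no EOT visit who dies after day 4, since that patient is still scored at the last infusion.
4. Change Table 3 so that sensitivity analysis 2 is run in All Treated, matching Table 15.

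The cost is SAP wording, one table row, and one short additional analysis with a listing. Death and infusion dates are already collected. The downside is that the primary response rate may fall slightly.
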